1. INTRODUCTION

The purpose of this statistical analysis plan (SAP) is to describe the procedures and the statistical methods that will be used to analyze and report results for Protocol JS-OAP2-US01. This SAP has been developed based on the study protocol (Version 5.0 dated on February 10, 2017) and electronic case report forms (eCRFs) and has been updated according to the amendment of study protocol (Version 6.0, June 26, 2017).

1.1 STUDY OBJECTIVES

1.1.1 Primary Objective

The primary objective of the study is to evaluate the efficacy and safety of autologous adipose tissue derived mesenchymal stem cells (AdMSC) for the treatment of osteoarthritis.

1.2 STUDY ENDPOINTS

1.2.1 Primary Efficacy Endpoints

The co-primary endpoints are:

Using the following three co-primary efficacy variables, the joint functional improvement of knee joint will be evaluated and gatekeeping procedures will be used for these three hypothesis tests.

- 1) Change of WOMAC score from baseline at Month 6 (JointStem group)
- 2) Change of VAS score from baseline at Month 6 (JointStem group)
- 3) MRI improvement evaluation at Month 6 (JointStem group)

MRI improvement evaluation will be finally analyzed through the following two steps:

- Radiologist will compare and analyze MRI results before and after the administration of IP and write a report for each subject.
- Principal Investigator will evaluate MRI results of subjects as one of three conditions (a: improvement, b: no change, c: progress) based on the radiologist's report stated above.

1.2.2 Secondary Efficacy Endpoints

The secondary efficacy endpoints are:

- 1) JointStem group vs. positive control group
 - ① Change of WOMAC score from baseline at Month 6
 - ② Change of VAS score from baseline at Month 6
 - ③ Change of KOOS from baseline at Month 6
 - ④ Change of Lysholm Knee Scoring Scale from baseline at Month 6
 - ⑤ Change of IKDC from baseline at Month 6
 - ⑥ Change of RAND-36 Score from baseline at Month 6

- 2) JointStem group
 - ① Change of WOMAC score from baseline at Months 9 and 12
 - ② Change of VAS score from baseline at Months 9 and 12
 - ③ Comparison of MRI improvement evaluations between at Month 6 and at Months 12
 - ④ Change of Lysholm Knee Scoring Scale from baseline at Months 6, 9 and 12
 - ⑤ Change of KOOS from baseline at Months 6, 9 and 12
 - ⑥ Change of IKDC from baseline at Months 6, 9 and 12
 - ⑦ Change of RAND-36 Score from baseline at Months 6, 9 and 12

1.2.3 Safety Endpoints

Safety endpoints include:

- Clinical laboratory tests
- 12-lead Electrocardiogram (ECG)
- Physical examinations
- Vital signs
- Adverse events (AEs) and concomitant medications

1.3 SUMMARY OF THE STUDY DESIGN

1.3.1 General Study Design and Plan

This is a double-blind, randomized, controlled study to evaluate the efficacy and safety of JointStem for the treatment of osteoarthritis. Following a 2-week screening period, approximately 30 subjects will be randomly assigned into one of the following two arms in a 2:1 ratio (2 JointStem: 1 positive control):

- JointStem (1×10^8 cells/3mL)
- Positive control: Hyaluronic Acid

After each subject completes 6-month visit (Visit 6) and the data management team confirms all individual data have no issue, the individual database will be locked and the blinding will be

open for the statistical analysis. Only subjects who are randomized to JointStem group will then be scheduled for 9-month and 12-month follow-up visits (Visits 7 and 8).

The Schedule of Assessments is presented by Table 1.

Table 1 Schedule of Assessments

| | Screen. | Harv. | Treat. | 1 st Follow-up | | | | 2 nd Follow-Up | |
|--|---------|-----------------|--------|---------------------------|----|----|----------------|---------------------------|------------------------------|
| Blinding | N/A | Double Blinding | | | | | | Open ⁷ | |
| Visit | 1 | 2 | 3 | 4 | 5 | 6 | ET | 7 | 8 |
| Week / Month | W-7 | W-5 | 0 | M1 | M3 | M6 | <M6 | M9 | M12 or Final FU ⁶ |
| Informed consent | X | | | | | | | | |
| Medical and Medication History | X | X | | | | | | | |
| Demographic information | X | | | | | | | | |
| Complete physical examination | X | | X | | X | X | X ⁴ | X | X |
| Vital signs and weight | X | X | X | X | X | X | X | X | X |
| Hematology, serum chemistry, and urinalysis ¹ | X | | X | X | X | X | X ⁴ | X | X |
| Pregnancy test ² | X | | | | | X | X ⁴ | | X |
| HIV test for Screening | X | | | | | | | | |
| 12-lead ECG | X | | X | | | X | X ⁴ | | X |
| X-ray | X | | | | | | | | |
| Eligibility confirmation | X | X | | | | | | | |
| Randomization | | X | | | | | | | |
| Liposuction | | X | | | | | | | |
| Injection of final drug product | | | X | | | | | | |
| AE and concomitant medication assessment | | | X | X | X | X | X | X | X |
| MRI scan ³ | X | | | | | X | X ⁵ | | X |
| WOMAC | | | X | X | X | X | X ⁴ | X | X |
| VAS | X | | X | X | X | X | X ⁴ | X | X |
| Lysholm | | | X | X | X | X | X ⁴ | X | X |
| KOOS | | | X | X | X | X | X ⁴ | X | X |
| IKDC | | | X | X | X | X | X ⁴ | X | X |
| Quality of Life (RAND-36) | | | X | | X | X | X ⁴ | X | X |

1. See Appendix 1 for the complete list of laboratory tests
2. Serum pregnancy test is performed for all females of childbearing potential (please refer to the relevant inclusion criteria)
3. May be performed the day of Visit 2 or after due to scheduling or re-scanning.
4. Performed only if the early termination is after V3.
5. Performed only if the early termination is after V4.
6. Performed if the follow-up is discontinued after V6.
7. Only for JointStem group.

1.3.2 Randomization and Blinding

As this is a double-blinded study, blinding of the drug contents from the subjects, investigators, and other study personnel at each clinical site is necessary. Because two syringes of JointStem and positive control are different, one physician must be only assigned to the role of syringe injection in order to maintain the double-blinding against other site physicians and staffs.

A subject will be assigned with one randomization code on Visit 2 (Week -5). After each subject completes Visit 6 (Month 6) and the data management team confirms all data have no issue, the randomization codes will be open for the statistical analysis.

A code-break envelope for each subject including the randomization code information will be retained by each site and can be opened, revealing the randomization information, for emergency purposes only. Investigator should note that the occurrence of a serious adverse event (SAE) should not routinely precipitate immediate unblinding. An attempt to contact the sponsor must be made prior to unblinding. If unblinding occurs, the subject must be early terminated; a written explanation must be prepared immediately.

1.3.3 Sample Size and Statistical Power Considerations

There was no formal sample size calculation since this is a proof-of-concept study and is not a hypothesis-driven study. The number of enrolled subjects is predefined at n=30, for 20 subjects per study group and 10 subjects per control group.

1.3.4 Interim Analysis

When at least 15 subjects complete 6-month visits (Visit 6, Month 6), one unblinded interim analysis can be performed to evaluate the efficacy and safety of JointStem without the suspension of subject enrollment. No adjustment on the overall alpha-level will be made, as this is not a statistically powered study. The interim analysis is not covered by this SAP.

2. STATISTICAL METHODS

2.1 GENERAL CONSIDERATIONS

In general, continuous variables will be summarized by number of subjects, mean, SD, median, minimum, and maximum values. Categorical variables will be summarized by counts and percentage of subjects in each category. Source data for the summary tables and statistical analyses will be presented as subject data listings, which include data collected on the electronic case report forms (eCRFs) as well as any derived variables for all enrolled subjects.

2.1.1 Reporting Precision

Summary statistics will be presented to the following degree of precision, unless otherwise specified:

| Statistics | Degree of Precision |
|--|--|
| Mean, Geometric mean, Median, Quartiles, Confidence limit boundaries | One decimal place more than the raw data. |
| Standard deviation, Standard error | Two decimal places more than the raw data. |
| Minimum, Maximum | The same as the raw data. |
| p-value | Rounded to 4 decimal places and therefore presented as 0.xxxx; p-values smaller than 0.0001 as '<0.0001'; p-values greater than 0.9999 as '>0.9999'. |
| Percentage | One decimal place. A percentage of 100% will be reported as 100%. Percentages of zero will be reported as 0. |

For weight and height, one decimal place will be used for summary statistics. Fractional numeric values will be presented with a zero to the left of the decimal point (for example, 0.12 – 0.30).

2.2 DEFINITIONS OF ANALYSIS POPULATIONS (ANALYSIS SETS)

2.2.1 Intention-To-Treat Population (ITT)

An intention-to-treat (ITT) population will include subjects who received the intra-articular injection and have at least post-injection efficacy measurements.

2.2.2 Per-Protocol Population (PP)

All subjects valid for ITT who completed Visit 6 (Month 6) will be 'valid per protocol' (also called 'valid for efficacy'). Additional criteria may be added prior to unblinding the study database.

2.2.3 Safety Population

A Safety population will include any subject who was randomized and completed Visit 2 (Week - 5, at which time adipose tissue was be harvested).

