#### **3.5.2 Identity of Investigational Product**

JointStem is a 5 ml syringe including AdMSCs as  $1 \times 10^8$  cells/3mL and is stable at refrigerated condition up to 1 week. A positive control syringe including hyaluronic acid will be purchased and packed by the aluminum foil pack to be matched with JointStem syringe in appearance to be indistinguishable.

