#### 4.2.2 Preparation of Final Drug Product in Biostar SCRI

The following procedures for the preparation of final drug product will be performed by well-trained lab technicians at Biostar SCRI. The official package containing the final drug product (syringes) will be shipped to the clinical site.

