##### 6.1.1.3 Safety Population

Any subject who was randomized and completed Visit 2 (Week -5) will be included in the evaluation of safety. This cohort will be evaluated for all safety variables.

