7. SAFETY ANALYSIS

All safety analyses will be performed for safety population. Statistical tests are not planned for safety variables. Safety assessments include:

- AEs
- Clinical laboratory tests
- ECG
- Physical examinations
- Vital signs

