7.1 ADVERSE EVENTS

AEs will be coded by SOC and PT using the MedDRA (Version 18.1). The verbatim term will be included in the AE listing.

A treatment-emergent adverse event (TEAE) is defined as an AE that occur or worsen on or after the injection of study drug and before the end of the study. Only TEAEs will be included in summary tables. All AEs, treatment emergent or otherwise, will be presented in subject data listings.

The TEAEs will be summarized as the number (percentage) of subjects with TEAEs within SOC and PT. Subjects who report the same PT on multiple occasions will be counted once for the PT: under the highest severity (severe > moderate > mild) when summarized by severity and under the closest relationship to study drug when summarized by relationship. If a subject reports multiple PT for a SOC, the subject will be counted only once for that SOC.

TEAEs will be summarized as below.

- An overview table, including number of subjects with
 - TEAEs
 - serious AEs (SAEs)
 - study drug related TEAEs
 - TEAEs by severity
 - TEAEs leading to study discontinuation
 - TEAEs leading to death
- TEAE by SOC and PT
- TEAE by SOC, PT, and Severity
- Study drug related TEAEs by SOC, PT
- SAEs by SOC and PT
- TEAEs leading to study discontinuation by SOC and PT

All AE tables will be sorted by SOC and PT in decreasing frequency of the number and percentage of subjects summarized by treatment group and total.

Missing date will be imputed followed table describes how missing date information will be handled:

| Partial Missing Start or Stop Date | Imputed Start Date | Imputed Stop Date |
|--|--|-----------------------------------|
| Missing month and day, and the year is present | January 1 of that year or first dose date if the year is the same as the year of first dose date | December 31 of that year |
| Missing day, but year and month are present | First day of that month or first dose date if the year and month are the same as the year and month of first dose date | Last day of that month |
| Missing month, but year and day are present | Missing month imputed as January | Missing month imputed as December |

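### TEAE percentages count only events on or after injection but divide by everyone harvested at Visit 2, so any subject harvested and not injected lowers the reported rates

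*SAP*

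**What the plan says.** The set used for safety does not depend on injection. SAP 2.2.3 states: "A Safety population will include any subject who was randomized and completed Visit 2". Protocol 6.1.1.3 agrees: "Any subject who was randomized and completed Visit 2 (Week -5) will be included in the evaluation of safety". SAP 7 then applies this set throughout: "All safety analyses will be performed for safety population".

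The event definition does depend on injection. Under SAP 7.1 a TEAE "is defined as an AE that occur or worsen on or after the injection of study drug and before the end of the study". The same section adds "Only TEAEs will be included in summary tables", and presents them as numbers and percentages of subjects. Events before injection appear only in listings.

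No safety set limited to injected subjects is defined. The ITT set (SAP 2.2.1) requires injection but also a post-injection efficacy measurement, and the PP set is a subset of ITT. The disposition table (SAP 3.1) has no row for subjects injected. Injection itself is only listed (SAP 5.1).

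**The concern.** The numerator and denominator of the TEAE percentages describe different groups. Someone who completed harvest but was never injected cannot have a TEAE by definition, yet is counted among those at risk of one.

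The protocol leaves room for such subjects. Injection at Visit 3 may come up to 5 weeks after Visit 2 (protocol 4.2.3). The screening MRI may be done on the day of Visit 2 or later, provided the result is known before injection (protocol 4.1), and a scan showing no cartilage damage is exclusion criterion 25. So a subject can be randomized, harvested, counted in the safety set and then found ineligible. Withdrawal under protocol 3.3 can also fall in this interval.

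No tests are planned for safety variables, so these descriptive percentages are the main between-arm summary of adverse events. If the denominator includes unexposed subjects, the frequency of events after the injection is understated. If the unexposed are unevenly spread, the side-by-side comparison is distorted as well.

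**Working it through.** The plan states no TEAE rate and no non-injection rate, so there is no figure of its own to reproduce.

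**Inputs**
- Arm sizes N: 20 JointStem and 10 control (protocol 6.2, SAP 1.3.3), which agrees with 30 subjects at 2:1.
- Uninjected subjects u: not in the documents. Assumed 0 to 4 of 20 for JointStem and 0 to 2 of 10 for control.
- TEAE rate r among injected subjects: not in the documents. Assumed 50%, with 20% and 80% as a range.

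**Step 1: dilution within an arm.** Reported rate = r × (N − u)/N.

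| Arm | u | Factor (N − u)/N | Reported if r = 20% | r = 50% | r = 80% |
|---|---|---|---|---|---|
| JointStem | 0 | 20/20 = 1.00 | 20.0% | 50.0% | 80.0% |
| JointStem | 1 | 19/20 = 0.95 | 19.0% | 47.5% | 76.0% |
| JointStem | 2 | 18/20 = 0.90 | 18.0% | 45.0% | 72.0% |
| JointStem | 4 | 16/20 = 0.80 | 16.0% | 40.0% | 64.0% |
| Control | 0 | 10/10 = 1.00 | 20.0% | 50.0% | 80.0% |
| Control | 1 | 9/10 = 0.90 | 18.0% | 45.0% | 72.0% |
| Control | 2 | 8/10 = 0.80 | 16.0% | 40.0% | 64.0% |

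Each uninjected subject takes 1/20 = 5% off every JointStem TEAE percentage, or 1/10 = 10% off every control percentage, in relative terms.

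**Step 2: effect on the comparison, with a true 50% in both arms.**
- Only JointStem loses 1, 2 or 4 subjects: 50 − 47.5 = 2.5, 50 − 45 = 5, or 50 − 40 = 10 points in JointStem's favour.
- Only control loses 1 or 2: 50 − 45 = 5 or 50 − 40 = 10 points in control's favour.
- Both arms lose the same fraction: no difference is created, but both rates are understated.

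**Step 3: how readily a loss could occur.** If each subject has the same assumed 5% chance of not being injected, the chance of at least one in an arm is 1 − 0.95^20 = 64% for JointStem and 1 − 0.95^10 = 40% for control. The expected factor is 0.95 in both. At an assumed 2% these chances are 33% and 18%; at 10% they are 88% and 65%.

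**Step 4: the same counts over injected subjects.** Ten JointStem subjects with a TEAE: 10/20 = 50.0% becomes 10/19 = 52.6%, 10/18 = 55.6% or 10/16 = 62.5% with 1, 2 or 4 uninjected. Five control subjects: 5/10 = 50.0% becomes 5/9 = 55.6% or 5/8 = 62.5% with 1 or 2 uninjected.

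**The case against.** The strongest defence is that starting the safety set at Visit 2 is deliberate and sound, because liposuction carries its own risk. The listed safety endpoint is the incidence of adverse events and laboratory abnormalities, not only of those after injection. That justifies keeping the set. It does not justify using it for TEAE percentages, because events between harvest and injection are left out of every summary table. The wider set adds people to the denominator and no harvest events to the numerator.

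A second defence is that a reader could nearly recover the right denominator. Counts are shown with the percentages, the disposition table gives ITT numbers by arm, and injections are listed. This stands in part. The ITT number should be close to the number injected, but it omits anyone injected who has no later efficacy measurement. The planned withdrawal reasons are also not split into before and after injection.

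A third is scale. With 50% in each arm, the standard error of the difference is √(0.25/20 + 0.25/10) = 0.194, or roughly ±38 points at 95%. A shift of a few points is small beside that. This is fair and limits the weight of the point, but imprecision is no reason to keep an avoidable downward bias.

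A reader might go further and infer that the loss will fall mainly on JointStem and give it a false safety advantage. JointStem is made from the subject's own cells and is stable for up to 1 week refrigerated (protocol 3.5.2); after preparation, "The official package containing the final drug product (syringes) will be shipped to the clinical site". By contrast, "A positive control syringe including hyaluronic acid will be purchased". The documents do not support that step. They mention no failed or late preparation and give no rate. A late MRI result and withdrawal apply to both arms. One lost control subject also dilutes its arm twice as much as one lost JointStem subject. Heavier loss in the JointStem arm is a possibility only.

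**Conclusion.** The mismatch holds on the text of both documents. No sentence states the denominator of the TEAE percentages outright, but SAP 7 assigns all safety analyses to the safety set and no other safety set exists.

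The size is conditional: 5% relative per uninjected JointStem subject and 10% relative per uninjected control subject, assuming the safety set has the planned 20 and 10. It is zero if everyone harvested is injected. The direction of any distortion between arms cannot be told from the documents. The 10-point gap in JointStem's favour is the far end of an assumed range (4 of 20 lost, none in control) and should not be read as an expected value.

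The point is confined to TEAE percentages. By-visit means of laboratory values, vital signs and ECG use scheduled visits without imputation (SAP 2.3 and 2.4), so an uninjected subject adds no post-injection value to them.

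**What to change.** - In SAP 2.2.3 and 7.1, define the subjects who were given the intra-articular injection as a set of its own and make it the denominator for all TEAE percentages. Note the exception in SAP 7.
- Put matching wording in protocol 6.1.1.3, which assigns all safety variables to the Visit 2 cohort. Otherwise the SAP would depart from the protocol, and its section 9 statement of no major change would no longer be true.
- Keep the Visit 2 population for listings, and add a summary of adverse events from harvest to injection on that population. For this to be complete, the start of adverse event collection must be reconciled: protocol 3.6.3 counts visits after randomization, while protocol 7.2 counts from the first dose.
- In the disposition table (SAP 3.1), add the number injected and the number harvested but not injected, by arm and reason.

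The cost is aligned wording in two documents and modest table reprogramming. Injection is already recorded, so the new denominator needs no new data. The downside is that TEAE percentages may look slightly less favourable in any arm with uninjected subjects.

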2.3 TIME WINDOWS FOR ANALYSIS

For by visit safety or efficacy summaries, only scheduled visits will be analyzed.

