**Secondary Endpoints:**  
1) JointStem group vs. positive control group  
① Change of WOMAC score from baseline at Month 6  
② Change of VAS score from baseline at Month 6  
③ Change of KOOS from baseline at Month 6  
④ Change of Lysholm Knee Scoring Scale from baseline at Month 6  
⑤ Change of IKDC from baseline at Month 6  
⑥ Change of RAND-36 Score from baseline at Month 6  
2) JointStem group  
① Change of WOMAC score from baseline at Months 9 and 12  
② Change of VAS score from baseline at Months 9 and 12  
③ Comparison of MRI improvement evaluations between at Month 6 and at Month 12  
④ Change of Lysholm Knee Scoring Scale from baseline at Months 6, 9 and 12  
⑤ Change of KOOS from baseline at Months 6, 9 and 12

- ⑥ Change of IKDC from baseline at Months 6, 9 and 12
- ⑦ Change of RAND-36 Score from baseline at Months 6, 9 and 12
- 3) Incidence of adverse events and laboratory abnormalities

**Exploratory Endpoints:** Analysis of all efficacy scales and MRI results and the history of treatments and medications following 2 years after injection for all subjects who are injected and complete 6-month follow-up visit

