### **3.3 Removal of Subjects from Study**

Subjects may be withdrawn from the study for the following reasons:

- At their own request or at the request of their legally acceptable representative
- If, in the investigator's opinion, continuation in the study would be detrimental to the subject's well-being
- At the specific request of the sponsor

Also, subjects must be withdrawn for the following reasons:

- A significant violation of the protocol, as determined by the sponsor or the investigator
- Highly significant abnormalities in the laboratory results (Highly significant abnormalities generally follow lab related exclusion criteria, but a PI can determine the high significance on any abnormalities for the safety of subject)
- Use of any other investigational drugs (including placebo)
- Subjects enrolled in the current trial but taking any prohibited medication/therapy stated in the inclusion/exclusion criteria that, in the investigator's opinion, will interfere with the study outcome.
- Subject enrolled in the current trial but having a baby

If a subject prematurely withdraws from the study, the subject must return to the clinical site for the early termination visit. In all cases, the reason for withdrawal must be recorded in the electronic Case Report Form (eCRF) and in the subject's medical records.

Contact will be maintained with subjects who are removed due to an adverse event (AE) until it has been resolved or stabilized, and the information will be documented in the eCRF and in the subject's medical records.

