## **7.2 Reporting Procedures for All Adverse Events**

The investigator is responsible for ensuring that all adverse events (as defined in Section 7.1) observed by the investigator or reported by subjects after the first dose of each subject are properly captured in the subject’s medical records and reported on the eCRF.

Documentation must be supported by an entry in the subject’s file. A laboratory test abnormality considered clinically relevant, e.g., causing the subject to withdraw from the study, requiring treatment or causing apparent clinical manifestations, or judged relevant by the investigator, should be reported as an adverse event. Each event should be described in detail along with start and stop dates, severity, relationship to investigational product, action taken, and outcome

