7.2 CLINICAL LABORATORY PARAMETERS

Laboratory assessments (hematology, blood chemistry and urinalysis) are collected at Visits 1, 3, 4, 5, 6, 7 and 8 (Screening, Baseline, M1, M3, M6, M9 and M12) or Early Termination (only if the subject is early terminated after Visit 3) or Final Follow-up Visit:

- Chemistry: Total Bilirubin, Alkaline Phosphatase, Aspartate Aminotransferase (AST) (SGPT), Alanine Aminotransferase (ALT) (SGOT), Blood Urea Nitrogen (BUN), Creatinine, Glucose, Albumin, Total protein, Sodium, Potassium, Chloride, Bicarbonate, Calcium, HCG, HIV.
- Hematology: Hemoglobin, Hematocrit, RBC, WBC, MCV, MCH, MCHC, Neutrophils (absolute), Lymphocytes (absolute), Monocytes (absolute), Eosinophils (absolute), Basophils (absolute), Platelets, PT-INR.
- Urinalysis: Specific gravity, Color, Appearance, pH, Protein, Glucose, Ketones, Bilirubin, Blood, Leukocyte esterase, WBC, RBC, Epithelial cell, Bacteria, Hyaline casts.

All laboratory parameters will be presented in Système International (SI) units. Quantitative results (including actual value and change from baseline) will be summarized using descriptive statistics by baseline and post-baseline visit for each laboratory test group above. Laboratory test results were evaluated as normal, abnormal (not clinically significant) or abnormal (clinically significant). The number and percentage of subjects of each category will be summarized by time point, treatment and total for each parameter.

All laboratory data will be included in the listings. A pregnancy listing will be provided separately.

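### The SAP tabulates laboratory abnormalities only visit by visit, so the protocol's secondary endpoint of their incidence gets no any-time, per-subject count from the laboratory data

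*SAP*

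**What the plan says.** The third item under secondary endpoints in the protocol (Synopsis and Section 3.6.1) is "Incidence of adverse events and laboratory abnormalities".

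The SAP does not repeat that item. Its secondary list (1.2.2) ends with the within-JointStem efficacy changes. Its safety list (1.2.3) includes "Clinical laboratory tests" and adverse events but does not mention incidence. SAP 9 reports no major change from the protocol's planned analyses.

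SAP 7.2 sets out the laboratory analysis. "Laboratory test results were evaluated as normal, abnormal (not clinically significant) or abnormal (clinically significant"); then "The number and percentage of subjects of each category will be summarized by time point, treatment and total for each parameter". Quantitative values and changes from baseline are also summarised by visit. On listings it says: "All laboratory data will be included in the listings".

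SAP 2.3, the section on time windows, consists of one rule: "For by visit safety or efficacy summaries, only scheduled visits will be analyzed". SAP 2.4 plans no imputation for safety variables.

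On adverse events, Protocol 7.2 requires reporting of "A laboratory test abnormality considered clinically relevant, e.g., causing the subject to withdraw from the study, requiring treatment" and similar cases. Protocol 7.1.1 says that laboratory findings the investigator considers not clinically significant should not be recorded as adverse events.

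**The concern.** The natural reading of incidence is the share of subjects who have the abnormality at any time after injection. A count at each visit is a different quantity. It shows how many subjects were abnormal on that occasion, but not whether the subjects abnormal at Month 1 are the same ones at Month 3. Without that link the visits cannot be added up or averaged into an incidence.

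The by-visit table may also lack some results. The scheduled-visits rule keeps off-schedule samples out of it. Early Termination samples have their own column in the schedule, but no rule says where they are tabulated. Protocol 3.3 requires withdrawal for "Highly significant abnormalities in the laboratory results", and withdrawn subjects are asked back for an Early Termination visit with a blood draw, so some of these samples may come from subjects of particular safety interest.

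At stake is whether a named secondary endpoint has a prespecified analysis in a study with no DSMB (SAP 8.2).

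**Working it through.** The documents give no abnormality rate and no formal safety test, so there is no figure in the plan to reproduce. The check has two parts.

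**1. What each planned output can deliver**

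| Output | Unit | Restricted to scheduled visits? | Abnormalities covered |
|---|---|---|---|
| Laboratory category table (SAP 7.2) | Subjects, separately at each time point | Yes (SAP 2.3) | All three categories |
| TEAE tables (SAP 7.1) | Subjects, once per preferred term over the whole period | No; SAP 2.3 covers only by-visit summaries | Only those recorded as adverse events |
| Laboratory listings (SAP 7.2) | Individual results | No | All, but no counts |

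The word total in the SAP 7.2 table reads as the two arms pooled, as it does elsewhere in the SAP, and not as a total over visits. No any-time count, worst post-baseline category or shift table is planned. No row of the table above gives a per-subject, whole-period count that includes abnormalities judged not clinically significant.

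**2. Whether the by-visit percentages fix the any-time incidence**

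Inputs:
- Post-injection laboratory visits: k = 3 to Month 6 in both arms (Months 1, 3, 6); k = 5 to Month 12 in JointStem only (adding Months 9 and 12). Source: Protocol 3.5.8 and 3.6.3.
- Arm sizes: 20 and 10. Source: Protocol 6.2 and SAP 1.3.3.
- Share abnormal at each visit, p: not in the documents. Assumed 5%, 10% and 20%, equal at every visit, with all subjects attending.

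Formulas for the share abnormal at least once:
- Minimum (same subjects every time): p
- Independent visits: 1 − (1 − p)^k
- Maximum (different subjects every time): min(1, k × p)

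For p = 10% and k = 3: minimum 10%; independent 1 − 0.9³ = 27.1%; maximum 3 × 10% = 30%.

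| Assumed p | To Month 6, k = 3: min / independent / max | To Month 12, k = 5: min / independent / max |
|---|---|---|
| 5% | 5% / 14.3% / 15% | 5% / 22.6% / 25% |
| 10% | 10% / 27.1% / 30% | 10% / 41.0% / 50% |
| 20% | 20% / 48.8% / 60% | 20% / 67.2% / 100% |

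In subjects: if 2 of 20 JointStem subjects are abnormal at each visit, between 2 and 6 have been abnormal by Month 6 (10% to 30%) and between 2 and 10 by Month 12 (10% to 50%). If 1 of 10 control subjects is abnormal at each of three visits, between 1 and 3 have been (10% to 30%). The planned table looks the same at either end of each range.

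The Month 12 column has no control counterpart. A whole-study comparison would set five chances to be abnormal against three, so the between-arm display has to stop at Month 6.

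**The case against.** The case against has several parts, and much of it stands.

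- **The adverse event route.** A reader might infer that abnormalities outside scheduled visits disappear from every table, or that subjects withdrawn for laboratory reasons are left out and the safety profile looks cleaner than it was. The documents do not support either reading. Protocol 7.2 requires clinically relevant abnormalities to be reported as adverse events, gives withdrawal as its first example, and sets no condition on visit type. SAP 7.1 counts treatment-emergent events per subject and plans a separate table of those leading to discontinuation. This covers most clinically significant abnormalities. It does not cover those judged not clinically significant, and it gives no summary by laboratory parameter.
- **The protocol's own display.** The Synopsis says safety variables are summarised by treatment group and visit, Protocol 6.1.6 details adverse event rates only, and neither document defines incidence for laboratory values. The any-time reading is therefore the usual one but is not stated. Even so, a by-visit display alone leaves the word incidence without an analysis.
- **Off-schedule samples are assumed.** No section describes unscheduled laboratory tests. This stands, so the point is limited to any that occur.
- **Early Termination and Final Follow-up.** Final Follow-up shares the Month 12 column in both schedules, and SAP 7.2 names both visits as collection points. Nothing calls them unscheduled. What remains is that the SAP does not say at which time point Early Termination results are tabulated, or that Final Follow-up is analysed as Month 12.
- **Size.** With about 30 subjects, the count can be made by hand from the listings. That limits the harm, but a listing is not a prespecified endpoint analysis.

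**Conclusion.** The point holds in a limited form. A named secondary endpoint has only a partial analysis: abnormalities are counted at each scheduled visit, and clinically relevant ones should be counted per subject as adverse events, but no any-time, per-subject incidence is calculated from the laboratory data. It would be too strong to say that the endpoint is never calculated in any form.

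The clear gap is abnormalities not recorded as adverse events, chiefly those judged not clinically significant, plus any off-schedule or Early Termination result without an assigned time point.

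The size depends on assumed rates. At 10% per visit the by-visit table is compatible with 10% to 30% of subjects by Month 6 and, in JointStem, 10% to 50% by Month 12. These ranges assume a constant share per visit and full attendance. No hypothesis test is affected, since none is planned for safety (SAP 7).

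**What to change.** - In SAP 7.2, add a table by arm and parameter giving the number (%) of subjects with at least one post-injection abnormality of either kind and, separately, with at least one clinically significant abnormality (worst post-baseline category). A table limited to clinically significant values would miss the main gap.
- Use scheduled, any unscheduled, Early Termination and Final Follow-up results.
- Show injection to Month 6 for both arms, and later JointStem data separately.
- State the denominator. The safety population is defined from Visit 2 (SAP 2.2.3) and can include subjects who were never injected.
- State in SAP 2.3 that the scheduled-visits rule does not restrict this table, and say where Early Termination and Final Follow-up results go in the by-visit tables.
- Restore the incidence of laboratory abnormalities to the SAP's endpoints.

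The cost is SAP wording and one more table from data already collected, with no change to study procedures. The reported incidence may exceed any single by-visit percentage, which a footnote can explain.
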